6.3 Safety Population

The safety population will consist of any subject receiving a dose of LMIS 25 mg.

6.4 Electrocardiogram (ECG) Population

The ECG population will consist of any subject receiving at least one dose of LMIS 25 mg and who had an ECG value measured for at least 1 post dose time point.

6.5 Pharmacokinetic/Electrocardiogram (PK/ECG) Population

The PK/ECG population will consist of any subject in the ECG population with post dose time-matched serum concentrations of leuprolide or testosterone.

The analysis of study population will be summarized in [Table 14.1.1](#). Besides, subjects excluded from the analysis will be listed in [Listing 16.2.3](#).

7. DISPOSITION OF PATIENTS AND STUDY COMPLETION

Data on the study completion status and primary reason for study discontinuation will be listed in [Listing 16.2.1](#). All subjects' disposition and completion status will be summarized in [Table 14.1.1](#). Individual subject eligibility will be listed in [Listing 16.2.2.1](#). All protocol deviation(s) will be listed in [Listing 16.2.2.2](#).

8. DEMOGRAPHICS AND OTHER BASELINE CHARACTERISTICS

Demographics information (Age (years), Gender, Race and Ethnicity) will be listed in [Listing 16.2.4.1](#). Demographics information and baseline characteristics included: Age (years), Gender, Race, Ethnicity, Diagnosis (days) of prostate carcinoma history, each TNM of prostate carcinoma history and ECOG performance will be summarized in [Table 14.1.2](#).

8.1 Tumor History and Medical History

Medical history and concurrent medical conditions data will be listed by subject as following:

[Listing 16.2.4.2](#): Tumor History

[Listing 16.2.4.3](#): Other Tumor History

[Listing 16.2.4.4](#): Previous Treatment of Malignant Disease

[Listing 16.2.4.5](#): Medical/ Surgery History

Statistical Analysis Plan

Listing 16.2.4.6: Previous Blood Donation

9. EFFICACY ANALYSIS

9.1 Primary Efficacy Variable

The primary endpoint of efficacy is to determine the percentage of subjects with a serum testosterone concentration suppressed to castrate levels (≤ 50 ng/dL) on Day 28 ± 1 day (week 4) following the first injection of LMIS 25 mg and to determine the proportion of subjects with serum testosterone suppression (≤ 50 ng/dL) from Day 28 ± 1 day (week 4) through Day 168 ± 5 days (week 24) until the end of the study.

The percentage of subjects with a serum testosterone concentration suppressed to castrate levels (≤ 50 ng/dL) on Day 28 ± 1 day (week 4) and on Day 168 ± 5 days (week 24) will be analyzed using a standard large sample normal approximation to a Binomial distribution and it will be summarized as count, percentage and exact 95% CI for binomial proportion.

The percentage of subjects with testosterone suppression (≤ 50 ng/dL) from Day 28 (week 4) through Day 168 ± 5 days (week 24) will be analyzed using the Kaplan-Meier approach. In this analysis an event is defined as occurring in subjects with a testosterone level > 50 ng/dL between Day 28 (week 4) and Day 168 (week 24). To accommodate drop-out and missing values the following censoring rules will be observed:

Table 9.1-1 Data Censoring Rules

Subject Discontinued	Day 28- 168 or Day of Discontinuation		To Be Handled As
	More Than 1 Missing Testosterone Value	Any Escape*	
Yes	No	No	Censored on day of last measurement
Yes	No	Yes	Event on day of first escape
Yes	Yes	No	Censored on day of last measurement before the first missing

Statistical Analysis Plan

Yes	Yes	Yes	Event on day of first escape
No	No	No	Censored on Day 168
No	No	Yes	Event on day of first escape
No	Yes	No	Censored on day of last measurement before the first missing
No	Yes	Yes	Event on day of first escape
No suppression by Day 28			Event on Day 28

*The escape (event) is defined as subject with a testosterone level >50 ng/dL

The testosterone level will be listed by subject and visit in [Listing 16.2.6.1](#).

The duration of time to reach a serum testosterone of >50 ng/dL is calculated from Day 28 to Day 168 or Day of Discontinuation. The duration of time to reach a serum testosterone of >50 ng/dL will be summarized and presented as number of subjects with event (event number), percentage of subjects with event, suppression rate by day 168 along with 95% confidence interval, mean, median and 95% confidence interval for median. A positive outcome to the study will be achieved if the lower 95% confidence interval bound for the response rate at Day 168 is greater than 90%.

Subjects exhibiting post-suppression breakthrough of serum testosterone to >50 ng/dL will also be summarized based on a subset for subjects who reach castration on day 28. The calculation formula is: [The subjects exhibiting post-suppression excursions of serum testosterone to >50 ng/dL at specific visit] / [The total number of subjects who reach castration at day 28 and has nonmissing serum testosterone value at specific visit] x 100%. It will be summarized as count, percentage and exact 95% CI for binomial proportion.

The summary of primary efficacy analysis will be presented as following:

[Table 14.2.1](#): Summary of Subjects with a Serum Testosterone Concentration Suppressed to Castrate Levels (ITT Population)

[Table 14.2.2](#): Summary of Subjects with Serum Testosterone Suppression Maintained from Day 28 through Day 168 (ITT Population)

[Table 14.2.3](#): Summary of Subjects Exhibiting Post-Suppression Breakthrough of Serum Testosterone to >50 ng/dL (ITT Population)

Table 14.2.13: Summary of Subjects with a Serum Testosterone Concentration Suppressed to Castrate Levels (PP Population)

Table 14.2.14: Summary of Subjects with Serum Testosterone Suppression Maintained from Day 28 through Day 168 (PP Population)

Table 14.2.15: Summary of Subjects Exhibiting Post-Suppression Breakthrough of Serum Testosterone to >50 ng/dL (PP Population)

Also, the Kaplan-Meier curve for duration of time to reach a serum testosterone of >50 ng/dL will be presented in Figure 14.2.1 and Figure 14.2.2 for ITT and PP populations.

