4.3. Withdrawal Criteria

Discontinuation from study is defined as discontinuation of all study visits and examinations. Participants may voluntarily withdraw from the study for any reason at any time. They may be considered withdrawn if they state an intention to withdraw, or fail to return for visits, or become lost to follow up for any other reason.

Subjects will be withdrawn from the study if any of the following occurs during the study period, i.e. from screening visit to the end of study (EOS):

- (1) Lost to follow-up
- (2) Subject withdrew consent
- (3) In investigator's opinion that treatment with prohibited medications is needed
- (4) Adverse event/serious adverse event
- (5) Protocol violation (please provide specific reason)
- (6) Lack of efficacy as determined by investigator
- (7) Subjects with persistent, non-castrate serum testosterone levels (>50 ng/dL)
- (8) Other

Subjects who are withdrawn due to AEs or SAEs will be followed until these events are resolved or until the event is considered stable.

Should a subject's testosterone concentration be above the castration level (> 50 ng/mL) at or after Visit 9 (Day 28/week 4), an extra visit for confirmation of testosterone level will be issued immediately. Subjects will be withdrawn from the study at the time of confirmation from the repeat testosterone analysis. The investigators can provide other alternative treatments promptly to these withdrawn subjects in accordance with standard clinical practice.

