7.2.1. Hormone level

Serum testosterone will be examined at the screening visit for eligibility (> 150 ng/dL). The screening sample of testosterone for eligibility will be sent to the Central Lab for analysis using a validated commercial assay. Thereafter, the serum testosterone can be sent to the Central Lab for analysis at the investigator's discretion. The serum testosterone will also be measured at baseline (Day 0) and at each visit for analysis at the Bioanalytical Lab. Blood samples will be collected from approximately 133 subjects in the study.

After enrollment, serum testosterone concentration in all subjects will be determined at baseline (Day 0) and at specified time points and will be sent for analysis at the Bioanalytical Lab. Blood samples for serum testosterone concentration measurement will be collected from all 133 subjects in the present study.

Serum testosterone concentrations will be measured by a validated LC/MS/MS method. The method validation follows the European Medicines Agency (EMA) Guideline on Bioanalytical Method Validation (EMA/CHMP/EWP/192217/2009) and the FDA Guidance for Industry: Bioanalytical Method Validation, May 2001.

For a faster sample turn-around, additional serum testosterone samples can also be analyzed by a validated, commercial diagnostic method. Additional testosterone tests (by a commercial method) will be ordered at a routine frequency of no more than monthly, which is consistent with standard medical practice for leuprolide therapy for the purpose of safety monitoring. More frequent tests may be ordered by the investigators at their discretion.

Serum samples for LH concentrations will be analyzed at the BA lab using a validated ELSIA method. More frequent tests of LH may be ordered by the investigators at their discretion, and these samples can be analyzed at the Central Lab for a faster data turn-around.

To establish the extended serum PK/PD relationship between leuprolide and testosterone levels, blood samples for determining the serum testosterone concentrations will be collected in the first enrolled 30 subjects on Day 0 (prior to the first dose of LMIS 25 mg and 2 h, 4 h, and 8 h post dose), Days 1, 2, 3, 7, 14, 21, 28, 42, 56, 77, 84 (week 12: prior to the second dose and 2 h, 4 h, and 8 h post dose), Days 85, 86, 87, 98, 112, 126, 140, 161, 168 (week 24) and Day 182 (week 26).

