10. STATISTICAL CONSIDERATIONS AND ANALYTICAL PLAN

10.1. Sample Size

Approximately 133 subjects are expected to be enrolled in this study. A sample size of 120 will achieve 85% power to detect a difference (P1-P0) of 0.0700 by using a one-sided binomial test. The target significance level is 0.0250. This assumes that the population proportion under the null hypothesis is 0.9000 and under the alternative to be 0.97. The estimated drop-out rate is 10%, so approximately 13 subjects may drop out from the study before Day 168 (week 24).

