4.4 Sample size estimation and power

Approximately 133 subjects are expected to be enrolled in this study. A sample size of 120 will achieve 85% power to detect a difference (P1-P0) of 0.0700 by using a one-sided binomial test. The

target significance level is 0.0250. This assumes that the population proportion under the null hypothesis is 0.9000 and under the alternative to be 0.97. The estimated drop-out rate is 10%, so approximately 13 subjects may drop out from the study before Day 168 (week 24).

Currently, there are totally 144 subjects enrolled in this study.

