9.3 Sensitivity Analysis

The sensitivity analysis for primary efficacy endpoint will be performed by excluding all subjects from site CZ03 due to GCP compliance issues at this site. These subjects will be excluded from

both ITT and PP populations as another analysis scenario (ITT excluding subjects from site CZ03, and PP excluding subjects from site CZ03) for sensitivity analysis.

The summary results will be presented as Table 14.2.25~Table 14.2.26 and Table 14.2.27~Table 14.2.28 for ITT and PP populations.

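### The primary analysis censors efficacy-related withdrawals like any other dropout, and no planned sensitivity analysis tests the effect

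*SAP*

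**What the plan says.** SAP 9.1 sets the criterion, with 90% as the threshold: "A positive outcome to the study will be achieved if the lower 95% confidence interval bound for the response rate at Day 168 is greater". The rate comes from Kaplan-Meier, and the event is a testosterone level above 50 ng/dL between Day 28 and Day 168.

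Table 9.1-1 (repeated from Protocol Table 5) sorts subjects by three things only: whether they discontinued, whether more than one testosterone value is missing, and whether there was an escape. A discontinued subject with no escape and at most one missing value is "Censored on day of last measurement". With more missing values he is censored earlier, at the last measurement before the first gap. The reason for discontinuation is not used.

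Protocol 4.3 gives as separate withdrawal reasons need for prohibited medication (item 3), "Lack of efficacy as determined by investigator" (item 6) and persistent non-castrate testosterone (item 7). Protocol 8.2 includes anti-androgens, other gonadotropin-releasing hormones and other prostate cancer treatments among the prohibited medications.

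On assays, Protocol 7.2.1 sends scheduled samples to the bioanalytical laboratory for LC/MS/MS, shipped in batches. For the Central Lab, after screening, it says "Thereafter, the serum testosterone can be sent to the Central Lab for analysis" when the investigator chooses. The escape footnote to Table 9.1-1 names no laboratory, and SAP 11.5 says only that unscheduled assessments are listed.

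SAP 9.3 has one entry: "The sensitivity analysis for primary efficacy endpoint will be performed by excluding all subjects from site CZ03".

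**The concern.** Kaplan-Meier treats a censored subject as if his later course were that of the subjects still under observation. This is least credible for a man taken off study because the investigator judged the drug not to be working, or because he needed another hormonal or anticancer treatment. If such men would have escaped more often than those who stayed, the Day 168 rate is too high and so is the bound compared with 90%.

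Nothing else in the plan would show this. SAP 5.2 provides no imputation. The per-protocol set (SAP 6.2) requires two doses, so it removes men who left before Day 84 instead of counting them as failures, and it still censors those who left later.

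**Working it through.** **The plan's own figure.** SAP 4.4: "A sample size of 120 will achieve 85% power to detect a difference (P1-P0) of 0.0700 by using a one-sided binomial test", at a one-sided level of 0.025. Protocol 10.1 gives the rates: "This assumes that the population proportion under the null hypothesis is 0.9000 and under the alternative to be 0.97".

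- Exact binomial, N = 120: the smallest passing count is 115, since P(X ≥ 115 | 0.90) = 0.0160 and P(X ≥ 114 | 0.90) = 0.038. Power is P(X ≥ 115 | 0.97) = 0.847.
- Normal approximation: z = (0.07 − 1.96·√(0.90·0.10/120)) / √(0.97·0.03/120) = 1.048, so power is 0.853.

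The stated 85% reproduces. The design tolerates 5 failures in 120, against 0.03 × 120 = 3.6 expected at a 97% rate.

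**Inputs for the tipping calculation.** From the documents: 144 enrolled (SAP 4.4), 133 planned, 10% dropout (14 of 144, 13 of 133) and the 90% criterion. Assumed: dropouts spaced evenly over Days 35 to 155; 4 observed events, because 0.03 × 144 = 4.3 and 0.03 × 133 = 4.0; and the interval type.

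**Which interval.** The SAP names none. Protocol 1.3 reports 97.0% (92.2%, 98.9%) for the earlier 50 mg study, with 4 failures in 137. Ignoring censoring, log-log gives (92.4%, 98.9%) and linear gives (94.3%, 99.9%). Log-log fits that report, so it is the main case here. That is an inference from another trial.

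**Formulas.** S = Π(1 − d/n) over event times, with d events among n at risk. V = Σ d/(n(n − d)). Log-log lower bound = S^exp(1.96·√V/|ln S|). Linear lower bound = S − 1.96·S·√V.

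**N = 144, 14 dropouts, 4 events (two on Day 28, one each on Days 85 and 86).**

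- S = (142/144)(135/136)(134/135) = 0.9716.
- V = 2/(144·142) + 1/(136·135) + 1/(135·134) = 0.0002076.
- Lower bound = 0.9716^2.666 = 92.6%. Success.

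**The same data with 3 dropouts (Days 35, 90 and 155) recounted as events.**

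- S = (142/144)(141/142)(135/136)(134/135)(133/134)(126/127) = 0.9500.
- V = 0.0003761.
- Lower bound = 0.9500^2.099 = 89.8%. Not met. With 2 recounted it is 90.7%, still met.

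Spreading the 4 events evenly over follow-up as well gives 92.4% falling to 89.7%, which is the same conclusion.

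**Censored subjects to recount before the lower bound is 90% or below (10% dropout, even spread).**

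| N | Interval | Observed events | Number |
|---|---|---|---|
| 144 | log-log | 5 | 2 |
| 144 | log-log | 4 | 3 |
| 144 | log-log | 3 | 4 |
| 144 | log-log | 2 | 5 |
| 144 | linear | 4 | 5 |
| 133 | log-log | 4 | 2 (bound 89.97%) |

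The log-log numbers at N = 144 are one higher if dropout does not shrink the risk set, because 7 events among 144 fully followed give 90.07%. The N = 133 entry is borderline: 6 events among 133 fully followed give 90.2%.

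**The case against.** The strongest reply is that the plan already catches most failures. Protocol 4.3 orders an immediate extra visit when testosterone is above the castrate level at or after Day 28, and withdraws the subject on confirmation. Protocol 6.22 gives early withdrawals the end-of-study assessments, including testosterone. Every row of Table 9.1-1 with an escape is an event on the day of first escape, discontinued or not, and no suppression by Day 28 is an event. So a withdrawal under item 7 will normally be an event. This stands, and it makes the route narrow. It does not close it. Protocol 6.22 itself foresees men who refuse or cannot attend the final visit, a late sample may be back at or below 50 ng/dL, the two assays may disagree, and lack of efficacy is a judgment with no stated testosterone criterion.

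The endpoint is also testosterone and not clinical benefit. A man withdrawn under item 6 with castrate values is not shown to be a failure. Item 3 is broader still: the prohibited list in Protocol 8.2 includes insulin, supplements and unlisted over-the-counter drugs. This also stands. Counting such withdrawals as events is therefore a sensitivity scenario and not the correction of an error, and item 3 should enter only for prostate cancer treatments.

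A reader might infer that a subject withdrawn on a Central Lab value above 50 ng/dL is censored by rule. The documents do not say so. The footnote, read plainly, would make any such value an escape. The LC/MS/MS statements in SAP 3.1, and the safety-monitoring purpose given to the routine additional commercial-assay tests in Protocol 7.2.1, point the other way. The rule is undefined, and that is as far as the point goes.

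**Conclusion.** The point holds in a limited form. The censoring table ignores the reason for withdrawal, efficacy-related withdrawals can therefore be informatively censored in the favourable direction, and no planned analysis shows how much this matters. Separately, the status of Central Lab and unscheduled values as escapes is not defined.

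At 144 subjects with a log-log interval, 2 to 5 recounted subjects would move the bound to 90% or below, for 5 down to 2 observed events. With 4 events the number is 3, or 5 with a linear interval. These figures rest on 10% dropout spread evenly, on the number of observed events and on the interval type, none of which the SAP fixes apart from the dropout estimate.

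A reader might infer that two or three such withdrawals reverse the trial's result. The documents do not support that. They report no result and do not say how many subjects left under items 3, 6 or 7. The small numbers hold only near 97% observed suppression with a log-log interval, and the lowest figure at 4 events belongs to the planned 133, not the 144 enrolled.

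**What to change.** - **SAP 9.3.** Add a sensitivity analysis of the primary Kaplan-Meier endpoint in the ITT population. Count as events, on the withdrawal day, subjects withdrawn under Protocol 4.3 item 6; under item 7 if not already events; and under item 3 when the prohibited medication was an anti-androgen, another gonadotropin-releasing agent or other treatment for prostate cancer.
- **SAP 9.3.** Report the tipping number: how many censored subjects must be recounted as events to bring the lower bound to 90% or below.
- **Table 9.1-1 footnote.** Name the assay that defines an escape and say whether unscheduled values count, with one rule for withdrawn and continuing subjects. A rule admitting any laboratory's value for withdrawn subjects only would treat the two groups differently in the primary analysis.

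The cost is two extra runs and a footnote. The sensitivity estimate may be slightly lower than the primary one. Only analysis classification changes; withdrawal and patient management stay as they are.

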7.2. Efficacy Assessment

Efficacy assessments will be performed based on the study schedule (Table 1a and 1b). The primary endpoint of efficacy is to determine the percentage of subjects with a serum testosterone concentration suppressed to castrate levels (≤ 50 ng/dL) on Day 28 ± 1 day (week 4) following the first injection of LMIS 25 mg, and the proportion of subjects with serum testosterone suppression (≤ 50 ng/dL) from Day 28 ± 1 day (week 4) through Day 168 ± 5 days (week 24) until the end of the study.

The proportion of subjects exhibiting post-suppression breakthrough of serum testosterone to > 50 ng/dL from Day 28 ± 1 day (week 4) through Day 168 ± 5 days (week 24) until the end of the study will also be determined.

The secondary endpoints will determine the mean acute-on-chronic changes in serum testosterone level before injection of the second dose LMIS 25 mg on Day 84 (week 12) and on Days 85, 86, 87 (week 13), and 98 (2 weeks post the second injection). The percentage of subjects observed with acute-on-chronic (surge) effect on serum testosterone and LH levels just before the second dose administration and on Day 1 to Day 3 (Days 85, 86, 87) and 14 days (Day 98) post the second injection of LMIS 25 mg will be analyzed.

The effect of LMIS 25 mg on serum LH levels and the percentage of subjects with enhanced serum testosterone concentration suppression to ≤ 20 ng/dL on Day 28 ± 1 day (week 4) and on Day 168 ± 5 days (week 24) by LMIS 25 mg administration will also be determined. In addition, the effects of LMIS 25 mg on the percentage of subject with PSA relapse and the percentage of subjects that achieves normal serum PSA level will be determined at the end of study.

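### The SAP tabulates testosterone breakthrough visit by visit and gives no formula for the proportion of subjects breaking through over Days 28 to 168, which the protocol asks for

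*SAP*

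**What the plan says.** Protocol section 7.2 (Efficacy Assessment) sets the target: "The proportion of subjects exhibiting post-suppression breakthrough of serum testosterone" above 50 ng/dL is to be determined from Day 28 through Day 168. This is a count of subjects over a period. Protocol section 10.4.1 lists breakthrough among the analyses whose detail is left to the SAP.

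SAP section 9.1 supplies that detail. It restricts the analysis to subjects castrate on Day 28. The numerator is the subjects above 50 ng/dL at a given visit, and the denominator is "The total number of subjects who reach castration at day 28 and has nonmissing serum testosterone value at specific visit". The results go into Tables 14.2.3 (ITT) and 14.2.15 (PP), with exact 95% intervals. No any-visit formula is given. SAP section 1 says that the SAP prevails where it differs from the protocol.

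Two other provisions bear on the point:

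- Protocol section 4.3 calls for a repeat test after a value above the castrate level at or after Day 28, and then: "Subjects will be withdrawn from the study at the time of confirmation from the repeat testosterone analysis".
- SAP section 9.1 also reports, from the Kaplan-Meier analysis, the number and percentage of subjects with an event over Days 28 to 168 (Tables 14.2.2 and 14.2.14). Its Table 9.1-1 counts a subject not suppressed by Day 28 as an event on Day 28.

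**The concern.** The protocol names a cumulative proportion. The SAP formula gives a series of point prevalences, each on its own denominator. Followed as written, the tables titled as the summary of breakthrough would hold numbers that do not answer the protocol's question, and the SAP's precedence clause means the protocol wording does not rescue them.

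A clinician reading those tables wants to know how many men lost castration at any time after reaching it. Several small rows may give a more favourable impression than the single figure. The decision on trial success is not at stake: it rests on the lower 95% bound of the Day 168 response rate.

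**Working it through.** **1. Inputs.** Enrolled: 144 (SAP 4.4). Visit days after Day 28 through Day 168: 11 for all subjects (56, 77, 84, 85, 86, 87, 98, 112, 140, 161, 168), plus Days 42 and 126 in the first 30 only (protocol 3.1). Prior 50 mg study (protocol 1.3): 135 of 137 castrate by Day 28, 2 not castrate, and 2 later excursions, both after the second dose on Days 168 to 171.

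**2. The plan's own figures.** The documents give no planned breakthrough rate. The nearest design figure is the power statement: "A sample size of 120 will achieve 85% power to detect a difference (P1-P0) of 0.0700", "by using a one-sided binomial test", with rates given as "population proportion under the null hypothesis is 0.9000 and under the alternative to be 0.97" and "The target significance level is 0.0250".

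- Exact: for n = 120, the smallest r with P(X ≥ r | 0.90) ≤ 0.025 is 115; attained alpha is 0.0160 and power 0.847.
- Normal approximation: Φ[(0.07 − 1.96·√(0.90·0.10/120)) / √(0.97·0.03/120)] = Φ[(0.07 − 0.0537)/0.0156] = 0.853.

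The 85% reproduces. It implies about 3% total failures, so a handful of escapes is a realistic illustration.

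**3. Why the visit rows do not combine.**

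- *Repeat highs.* If 4 subjects are each high at two visits, the rows add to 8/144 = 5.6%, although only 4/144 = 2.8% broke through.
- *Withdrawal.* Subjects with a confirmed escape leave later numerators and denominators.
- *Unequal denominators.* One escape on Day 42 or 126 shows as about 1/30 = 3.3%. At a visit common to all it shows as 1/144 = 0.7%.

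**4. Size at the 11 common visits.** Assume 4 escapers, and all 144 castrate at Day 28 and measured throughout.

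| Quantity | Result | Exact 95% CI |
|---|---|---|
| Any breakthrough, 4/144 | 2.78% | 0.76% to 6.96% |
| Highest row, four brief escapes at four different visits, 1/144 | 0.69% | 0.02% to 3.81% |
| Highest row, all four high at one visit, 4/144 | 2.78% | 0.76% to 6.96% |

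The cumulative figure is therefore 1 to 4 times the highest row. Simulation under stated timing assumptions fills in the middle, as the ratio of the cumulative count to the expected highest row:

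- single-visit escapes at random visits: about 2.7 (expected highest row 1.02%);
- escapes lasting 2, 3 or 5 visits: about 1.9, 1.7 and 1.4;
- escapes confined to Days 85 to 87: 1.0 to 1.7.

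**5. Prior-study pattern.** Any breakthrough: 2/135 = 1.48% (exact 95% CI 0.18% to 5.25%). Highest row: 1/135 = 0.74% or 2/135 = 1.48%, so a factor of 1 to 2.

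**6. Kaplan-Meier event percentage against breakthrough.** In the prior study the events would be 2 + 2 = 4, and 4/137 = 2.92%. Breakthrough alone is 2/135 = 1.48%. The difference is the two Day 28 failures in the numerator and their place in the denominator.

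**7. Drop-out in a crude any-visit row.** The protocol plans for 10%: "The estimated drop-out rate is 10%, so approximately 13 subjects may drop out". Applied to 144, that is about 14. If all 14 left just after Day 28 without an escape, 4/144 = 2.78% would compare with 4/130 = 3.08% among those followed.

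**The case against.** The strongest reply is that the cumulative information is nearly all there. Tables 14.2.2 and 14.2.14 give subjects with an event over the whole period, and Tables 14.2.1 and 14.2.13 give the number castrate on Day 28. Subtracting the Day 28 failures recovers the breakthrough count, apart from missing Day 28 values, and Listing 16.2.6.1 shows every result. Breakthrough is not itself listed as a primary or secondary endpoint in protocol section 2.2, and a table shell, which the documents do not include, might carry an any-visit row. All of this limits the importance. It does not remove the mismatch: the stated formula gives another quantity, and the named one is left for the reader to rebuild without its interval.

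Three stronger readings are tempting, and the documents do not support them.

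- *That the rows understate breakthrough several-fold.* That needs brief escapes at different visits, or comparison with the average row. In the 4-of-144 example the average is 4/(11·144) = 0.25%, which is 11 times lower only because there are 11 visits. The only timing evidence, from the 50 mg product, points to clustering after the second dose.
- *That everyone who breaks through leaves the later rows.* Withdrawal follows a confirmed escape. The prior-study excursions were transient, and such subjects may stay in.
- *That the trial would hide breakthrough altogether.* The recovery described above shows otherwise.

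A fair criticism of the remedy also stands: a crude proportion counts early leavers without an escape as free of breakthrough.

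**Conclusion.** The point holds, at modest size. SAP section 9.1 states a per-visit rule where the protocol asks for a whole-period proportion of subjects, and the rows cannot be turned into that proportion.

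At visits common to all subjects with complete data, the highest row can equal the cumulative figure or fall below it. The factor is 1 to 4 for an assumed 4 escapers in 144, and 1 to 2 for the prior-study pattern. These factors rest on assumed counts, timing and duration, not on anything the plan fixes. At Days 42 and 126 the denominator of about 30 can push a row above the cumulative figure, so the direction is not uniform either.

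The Kaplan-Meier event percentage is close to the wanted quantity but mixes in Day 28 non-suppression. The primary success criterion does not change.

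**What to change.** In SAP section 9.1 and Tables 14.2.3 and 14.2.15:

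1. Add a row for subjects castrate at Day 28 with at least one testosterone above 50 ng/dL after Day 28 through Day 168, divided by all subjects castrate at Day 28, with an exact 95% CI.
2. Beside it, give the Kaplan-Meier cumulative incidence (one minus the Kaplan-Meier estimate) at Day 168 in the same subset, under the Table 9.1-1 censoring rules. The no-suppression-by-Day-28 line does not apply in this subset. Early leavers are then censored and not silently counted as free of breakthrough.
3. Keep the per-visit rows as supporting detail, showing each denominator so that Days 42 and 126 are read correctly.

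The cost is one or two table rows and a sentence or two of text, with no new data. The reported breakthrough rate may look less favourable than the visit rows alone.
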